1. STUDY DESIGN & OUTCOMES

Study Protocol TMI-09-01-E (the COMPASS Trial Extension) is a multicenter observational study. Up to 480 subjects randomized in the Study Protocol TMI-09-01 (the COMPASS Trial) at up to 24 investigational sites may participate. Study data through 5 years post-randomization in the COMPASS Trial will be collected for subjects who consent to participate.

This statistical analysis plan (SAP) presents the details of the statistical methodologies for the analysis of data for Study Protocol TMI-09-01-E (Version G, dated 26 October 2016). The purpose of this research study is to evaluate the long-term safety of the CyPass Micro-Stent in subjects who completed the COMPASS Trial.

Primary Outcome

- Rate of occurrence of sight-threatening adverse events (AE)

Secondary Outcomes – Safety

- Best Corrected Visual Acuity (BCVA)
- Rate of occurrence of ocular adverse events (AE)
- Slit lamp, gonioscopy and fundus findings
- Visual field loss mean deviation (MD)
- Central corneal thickness (CCT)
- Central corneal endothelial cell density (ECD)
- Rate of occurrence of CyPass movement, defined as a change by at least 1 in the number of CyPass rings visible (e.g., from 0 rings to 1 ring or from 3 rings to 2 rings) that does not result in clinical sequelae (e.g., secondary surgical intervention to modify device position, corneal endothelial touch by device, corneal edema leading to loss of BCVA > 2 lines at the last postoperative visit in comparison with preoperative BCVA, progressive corneal endothelial cell loss (ECL), erosion of device through sclera, or device obstruction requiring secondary surgical intervention), and that is not attributable to:
 - variations in gonioscopic viewing angle or illumination,
 - changes in angle anatomy due to concomitant findings such as resolution of hyphema,
 - changes in anterior chamber depth, or
 - development of focal peripheral anterior synechiae.

Secondary Outcomes – Effectiveness

- Mean change in intraocular pressure (IOP)
- Proportion of subjects who are not using ocular hypotensive medication with $\geq 20\%$ reduction in IOP from baseline in the COMPASS Trial
- Proportion of subjects who are not using ocular hypotensive medication with IOP ≥ 6 mmHg and ≤ 18 mmHg

2. ASSESSMENT SCHEDULE

Subjects are to be evaluated at 36 months (1095 ± 90 days), 48 months (1460 ± 90 days) and 60 months (1825 ± 90 days) post-randomization in study protocol TMI-09-01. Hereafter, the term “XT scheduled follow-up visits” refers to the 36, 48, and 60-month scheduled visits. The examinations required at each scheduled study visit are outlined and summarized in Appendix 1 (Schedule of Events and Procedures) and a description of examination methodology is provided in Appendix 2 (Examination Procedures, Tests, Equipment and Techniques) of the protocol.

“Baseline” is defined as the Baseline Visit of the COMPASS Trial, unless noted otherwise. Analysis of other visits from the COMPASS Trial (from the 3, 6, 12, and 24-month visits) will include only subjects who enrolled (satisfied study eligibility criteria and signed the informed consent form) in COMPASS-XT.

3. ANALYSIS POPULATION

The analysis population will consist of up to 480 eyes of 480 subjects who completed enrolled in COMPASS-XT

4. GENERAL STATISTICAL CONSIDERATIONS

Unless noted otherwise, continuous variables will be characterized with the number of non-missing values, means, standard deviations, medians, minimums, and maximums while categorical variables will be characterized by frequencies (numerators), denominators, and percentages. There are no hypotheses tested in this study. All confidence intervals will be 95% confidence intervals and will be two sided. Confidence intervals for continuous variables will be based on the t distribution. Confidence intervals for categorical variables be calculated using the exact Clopper-Pearson 95% binomial formula. If there is a special case for a one sided interval, then that interval will be a 97.5% one-sided confidence interval.

All statistical analyses will be conducted using SAS[®] software, Version 9.4 of the SAS System for Windows or higher.

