5.1 Sight Threatening Ocular Adverse Events

Sight-threatening AEs include, but are not limited to, BCVA loss of ≥ 3 lines, endophthalmitis, corneal decompensation, severe retinal detachment, severe choroidal hemorrhage, severe choroidal detachment and aqueous misdirection. A non-parametric time to event Kaplan-Meier (K-M) analysis for the sight-threatening AE rate at 5 years will be performed, stratified by treatment group. This method accounts for all information that discontinued subjects contribute

to the rate of the primary safety event up to the point at which that subject discontinues (i.e., is censored). The cumulative Kaplan-Meier probability and associated and 95% confidence intervals that a subject experienced a sight-threatening AE will be provided for each treatment group at 5 years.

To aid in the interpretation of the results, the annualized rates (percentages) for each year and over the 5-year period will also be calculated using the LIFETEST procedure. There will be no covariate adjustments in the model as the only factor will be treatment group.

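### SAP 5.1 gives a 5-year risk and interval for each arm but no CyPass-minus-Control difference with a confidence interval

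*SAP*

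**What the plan says.** The primary outcome in SAP 1 is the rate of sight-threatening adverse events. For it, SAP 5.1 plans the following: "A non-parametric time to event Kaplan-Meier (K-M) analysis for the sight-threatening AE rate at 5 years will be performed, stratified by treatment group". The cumulative probability and its 95% interval "will be provided for each treatment group at 5 years", with annualized rates alongside. The same section adds: "There will be no covariate adjustments in the model as the only factor will be treatment group". It specifies no contrast on that factor.

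SAP 4 sets the general rules. It says "There are no hypotheses tested in this study" and "All confidence intervals will be 95% confidence intervals and will be two sided". For binary outcomes, "Confidence intervals for categorical variables be calculated using the exact Clopper-Pearson 95% binomial formula", which is a single-proportion method. Continuous outcomes get t-based intervals. No method for a difference or ratio is named.

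Protocol 9.1 also stops at one Kaplan-Meier estimate per group. Protocol 4.2 describes the two groups: 505 subjects were randomized in the parent trial to cataract surgery with the device or to cataract surgery alone. The aim in Protocol 5 and SAP 1 is to evaluate the device's long-term safety.

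**The concern.** Every study eye had cataract surgery, so the event rate in the CyPass arm mixes what the surgery does with what the device does. The control arm is the only thing in the design that can separate them, and the quantity that does so is the between-arm difference. The plan collects the data for that quantity and then leaves it out.

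Two things are lost. The report will not state the excess risk with its uncertainty, and it will not say how large an excess the data can exclude. A safety study with few events is asked for the second of these most often. With two intervals side by side, the natural shortcut is to look for overlap. That shortcut is biased toward seeing no difference, which in a safety study is the unfavourable direction.

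**Working it through.** The documents give no sample-size calculation, power, margin or expected event rate, so there is no figure of the plan's to reproduce. The check measures how far overlap of two intervals departs from an interval for the difference.

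**Inputs**
- From the documents: two-sided 95% intervals (SAP 4); at most 480 subjects (SAP 1); two arms (Protocol 4.2).
- Assumed, because not stated: CyPass:Control allocation from 1:1 to 3:1; 5-year risks of 2% or 5% (Control) and 8% or 10% (CyPass); complete follow-up, so that the Kaplan-Meier estimate equals the simple proportion.

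**Step 1: large-sample rule.** Two 95% intervals fail to overlap only if the difference exceeds 1.96 × (SE1 + SE2). The interval for the difference excludes zero once it exceeds 1.96 × √(SE1² + SE2²). So non-overlap requires

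|z| > 1.96 × (SE1 + SE2) / √(SE1² + SE2²).

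- Equal SEs: 1.96 × 2/√2 = 2.77, two-sided level 0.0056.
- SE ratio 1.73: 1.96 × 2.73/2.00 = 2.68, two-sided level 0.0074.

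The overlap rule therefore works at about 0.006 to 0.007, not 0.05.

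**Step 2: worked example, 240 per arm (assumed).** CyPass 19/240 = 7.9%; Control 7/240 = 2.9%; difference 5.0 points.

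| Per-arm interval | CyPass | Control | Overlap? |
|---|---|---|---|
| Clopper-Pearson | 4.8 to 12.1% | 1.2 to 5.9% | yes |
| Kaplan-Meier, log-log | 5.1 to 12.1% | 1.4 to 6.0% | yes |

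Interval for the difference:
- Newcombe: the Wilson limits are 5.13 to 12.03% and 1.42 to 5.90%. Lower limit = 5.0 − √[(7.92 − 5.13)² + (5.90 − 2.92)²] = 5.0 − 4.1 = 0.9. Upper limit = 5.0 + √[(12.03 − 7.92)² + (2.92 − 1.42)²] = 5.0 + 4.4 = 9.4.
- Greenwood: SEs 1.74 and 1.09 points, combined 2.05. 5.0 ± 1.96 × 2.05 gives 1.0 to 9.0.
- Log-log limits combined in the same way as Newcombe: 0.8 to 9.5.

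All three exclude zero.

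**Step 3: unequal allocation (assumed 360 v 120).** 29/360 = 8.1% and 3/120 = 2.5%; difference 5.6 points. The per-arm intervals again overlap (Clopper-Pearson 5.5 to 11.4% and 0.5 to 7.1%). The difference interval now depends on the method: Newcombe 0.4 to 9.2, Greenwood 1.6 to 9.5, combined log-log −0.03 to 9.3. With three control events the choice of method decides the answer, so it needs to be fixed beforehand.

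**Step 4: how often it matters.** Exact binomial enumeration at N = 480 gives the chance that each approach shows the CyPass excess:

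| Assumed risks (Control v CyPass) | Approach | 1:1 | 2:1 | 3:1 |
|---|---|---|---|---|
| 2% v 8% | Newcombe CI for difference above zero | 88% | 80% | 70% |
| 2% v 8% | Clopper-Pearson intervals do not overlap | 55% | 46% | 36% |
| 5% v 10% | Newcombe CI for difference above zero | 54% | 46% | 37% |
| 5% v 10% | Clopper-Pearson intervals do not overlap | 20% | 17% | 12% |

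**Step 5: zero events.** With a true control risk of 2% and 120 controls, the chance of no control event is 0.98^120 ≈ 9%. The Greenwood variance for that arm is then zero and the log-log interval is undefined. A plain Greenwood difference would ignore the control arm's uncertainty altogether.

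**The case against.** The plan is internally consistent. It describes an observational study whose aim is to collect long-term safety data, and it sets no objective of estimating added risk over surgery alone and no margin to exclude. Describing each arm and testing nothing is a legitimate choice. That stands: the omission is no contradiction, and no planned result becomes wrong because of it. It does not dispose of the point, because the SAP already reports many intervals without tests and a difference with an interval is one more of the same kind.

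A reader might infer that the plan forces a judgement by overlap, or that the study cannot say how much risk the device adds. The documents do not support either. The SAP never tells anyone to compare intervals by overlap. Both 5-year estimates and their intervals will be reported, so the point difference follows by subtraction and an approximate interval can be worked out. The gap is that this is left to the reader, with the method chosen after the data are seen.

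A reader might also infer that the contrast would be a randomized comparison. It would not be, fully. Entry requires completing the parent trial (Protocol 7.1), early terminators are excluded (7.2), fresh consent is needed (8.1), and some visits may be filled from charts (8.2). This objection stands and must accompany the estimate. It is no reason to omit it, since two side-by-side arms carry the same selection.

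**Conclusion.** The point holds as a missing descriptive estimate, and it is worth correcting. Neither document plans a between-group difference or ratio with an interval for the primary outcome, although the comparison group is followed. The overlap shortcut acts at about a two-sided 0.006 level at equal standard errors. Under the assumed risks and allocations, it shows an excess 25 to 34 percentage points less often than a 95% interval for the difference.

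The general rule in Step 1 needs only a large-sample approximation. The percentages rest on assumed allocation, event risks and complete follow-up, none of which the documents give. The 240-per-arm example is robust to the interval method; the 360 v 120 example is not and should not be cited as proof of a hidden excess. Nothing here shows that the device carries an excess risk, or that the study would miss one if the reader derived the difference.

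**What to change.** In SAP 5.1, add the CyPass-minus-Control difference in 5-year Kaplan-Meier probability with a two-sided 95% CI, and specify:

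- **Method.** Name it in advance and choose one that remains valid with few events in an arm, for example combining log-log or score-type per-arm limits. State the fallback for an arm with zero events, including the denominator it uses. Do not rely on a plain Greenwood interval. Name the type of the per-arm Kaplan-Meier interval at the same time, since the SAP does not.
- **Status.** Label it descriptive, with no p-value. The no-hypothesis statement in SAP 4 can stay.
- **Caveat.** State beside the estimate that it compares parent-trial completers who consented to the extension, so randomization protects it only partly.

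Optionally, add the difference in mean endothelial cell density change, with a t-based 95% CI, at each extension visit in SAP 5.4 on the same terms. The proportion with at least 30% cell loss is not part of this fix. That threshold appears only within the device-malposition definition in Protocol 10.1, and no summary of it is planned, so it would be a new analysis needing its own justification.

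The cost is a few lines of code and a short SAP paragraph, with no extra subjects or visits. The downside is a contrast that could be read as fully randomized if the caveat is dropped.

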4.1 Subject Accountability

Subject accountability by study visit will be summarized based on ANSI Z80.27-2014, modified as necessary for an observational study. A listing of subjects who are screened and considered to be ineligible for study participation will be presented, based on data to be provided by the Alcon monitoring group. This listing will include the reason for subject ineligibility.

In addition, a summary table of protocol deviations will be provided.

4.2 Demographic and Baseline Characteristics

Demographic and baseline characteristics from the COMPASS Trial for the subjects who are enrolled into this study will be tabulated by treatment group and all subjects (i.e., the total). Age (in years) at consent of the COMPASS Trial will be analyzed as a continuous variable and by the following categories: <60 years, 60 to <70 years, 70 to <80 years, and ≥80 years. Gender, race, ethnicity, and study eye will be analyzed as categorical variables.

5. STATISTICAL METHODS

The objective of this study is to collect long-term safety data regarding the CyPass Micro-Stent in subjects who completed the COMPASS Trial. The primary outcome is the occurrence of sight threatening AEs. Other study outcomes include the incidence of ocular AEs in the study eye, BCVA, slit lamp, gonioscopy and fundus examination findings, central corneal thickness, central corneal ECD, CyPass movement, and intraocular pressure.

5.1 Sight Threatening Ocular Adverse Events

Sight-threatening AEs include, but are not limited to, BCVA loss of ≥ 3 lines, endophthalmitis, corneal decompensation, severe retinal detachment, severe choroidal hemorrhage, severe choroidal detachment and aqueous misdirection. A non-parametric time to event Kaplan-Meier (K-M) analysis for the sight-threatening AE rate at 5 years will be performed, stratified by treatment group. This method accounts for all information that discontinued subjects contribute

to the rate of the primary safety event up to the point at which that subject discontinues (i.e., is censored). The cumulative Kaplan-Meier probability and associated and 95% confidence intervals that a subject experienced a sight-threatening AE will be provided for each treatment group at 5 years.

To aid in the interpretation of the results, the annualized rates (percentages) for each year and over the 5-year period will also be calculated using the LIFETEST procedure. There will be no covariate adjustments in the model as the only factor will be treatment group.

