8.2 Study Visits

All subjects enrolled will return for defined follow-up visits through 60 months post-randomization in the COMPASS Trial. The number of scheduled study visits required will be dependent on the date of subject randomization in the COMPASS Trial. Data collected from each study visit will be recorded on an electronic Case Report Form (eCRF).

8.2.1 36 Month Postoperative Visit

This visit will occur at postoperative day 1095 ± 90 days. The following information will be captured for the study eye at this visit:

- Manifest refraction and ETDRS BCVA
- Slit lamp biomicroscopy
- Goldmann tonometry
- Dilated fundus examination and C:D ratio assessment
- Visual field mean deviation
- Gonioscopy examination (CyPass-implanted eyes only)
- Central corneal pachymetry
- Specular microscopy
- Ocular hypotensive medications
- AE assessment
- Subject Symptom Questionnaire

In the event a subject is enrolled who is more than 36 months postoperative, retrospective data for the 36-month follow-up period, if available, may be collected from review of the subject's medical chart.

**CYPASS® MICRO-STENT
PROTOCOL TMI-09-01-E VERSION G**

8.2.2 48 Month Postoperative Visit

This visit will occur at postoperative day 1460 ± 90 days. The following information will be captured for the study eye at this visit:

- Manifest refraction and ETDRS BCVA
- Slit lamp biomicroscopy
- Goldmann tonometry
- Dilated fundus examination and C:D ratio assessment
- Visual field mean deviation
- Gonioscopy examination (CyPass- implanted eyes only)
- Central corneal pachymetry
- Specular microscopy
- Ocular hypotensive medications
- AE assessment
- Subject Symptom Questionnaire

In the event a subject is enrolled who is more than 48 months postoperative, retrospective data for the 48-month follow-up period, if available, may be collected from review of the subject's medical chart.

8.2.3 60 Month Postoperative Visit

This visit must occur at postoperative day 1825 ± 90 days. The following information will be captured for the study eye at this visit:

- Manifest refraction and ETDRS BCVA
- Slit lamp biomicroscopy
- Goldmann tonometry
- Dilated fundus examination and C:D ratio assessment
- Visual field mean deviation
- Gonioscopy examination (CyPass-implanted eyes only)
- Central corneal pachymetry
- Specular microscopy
- Ocular hypotensive medications
- AE assessment
- Subject Symptom Questionnaire

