8.3 Unscheduled Visits

Unscheduled visits are clinic visits not specified in the protocol when the subject returns for examination due to a complaint regarding the study eye or a surgical procedure performed on the study eye. No specific testing is required at unscheduled visits; rather, the investigator and/or qualified investigational staff will perform the examinations or procedures necessary to evaluate the subject at these visits. Clinical data from unscheduled visits will be recorded on the relevant eCRF.

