8.4.2 Completed Subjects

Completed subjects are those who are not discontinued from the study prior to completion of required scheduled visits.

**CYPASS® MICRO-STENT
PROTOCOL TMI-09-01-E VERSION G**

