9.1 Sight Threatening Ocular Adverse Events

Sight-threatening AEs include, but are not limited to, BCVA loss of ≥ 3 lines, endophthalmitis, corneal decompensation, severe retinal detachment, severe choroidal hemorrhage, severe choroidal detachment and aqueous misdirection. A non-parametric time to event Kaplan-Meier (K-M) analysis for the sight-threatening AE rate at 5 years will be provided by treatment group. This method accounts for all information that discontinued patients contribute to the rate of the primary safety event up to the point at which that patient discontinues (i.e., is censored). The cumulative Kaplan-Meier probability that a subject experienced a sight-threatening AE will be completed for each treatment group. To aid in the interpretation of the results, the annualized rates for each year and over the five (5) year period will be calculated.

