5.2 Ocular Adverse Events

The number of subjects reporting at least one AE of a given type specified in the protocol will be summarized. Ocular AEs not specified in the protocol (i.e., recorded as “other” and written in rather than selected from the list) that occur during the study will coded by MedDRA preferred term and summarized. Each AE will be summarized by incidence (numerator), denominator, percentage and 95% confidence interval. The summarization will be conducted using the FREQ procedure and the count, percent and exact Clopper-Pearson 95% binomial confidence intervals will be reported. Protocol-specified and other AEs will also be provided in separate listings.

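### Does the 5-year Kaplan-Meier figure need stated event dates, completer censoring dates and a day number for 5 years?

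*SAP*

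**What the plan says.** SAP 5.1 and Protocol 9.1 call for a Kaplan-Meier analysis of sight-threatening adverse events by treatment group. The result is the probability that a subject "experienced a sight-threatening AE will be provided for each treatment group at 5 years", with a 95% confidence interval. Protocol 9.1 adds that "the annualized rates for each year and over the five (5) year period will be calculated".

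The only censoring statement concerns discontinued subjects, who contribute information "up to the point at which that subject discontinues (i.e., is censored"). Protocol 8.4.2 defines the rest: "Completed subjects are those who are not discontinued from the study prior to completion of required scheduled visits". A completer is therefore outside the stated rule.

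On timing, SAP 2 schedules the last visit at "60 months (1825 ± 90 days) post-randomization in study protocol TMI-09-01", and Protocol 8.2.3 says "This visit must occur at postoperative day 1825 ± 90 days". Randomization took place during surgery (Protocol 4.2), so the two time origins agree. SAP 6 excludes imputation and adds no rule on dates.

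**The concern.** One named component of the endpoint, loss of three or more lines of BCVA, may come to light only when acuity is measured. Protocol acuity tests are scheduled only at months 36, 48 and 60, and at other attendances "No specific testing is required at unscheduled visits". Some events may therefore carry no date except that of a scheduled visit.

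If such an event is dated at the visit, and an event-free completer is censored at the same visit, each completer leaves the risk set at the very examination that could have found an event. Across the 60-month window the number at risk then runs down towards one. Read at day 1825, the curve misses events found later in the window. Read at day 1915, it divides the late events by very small numbers.

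No hypothesis is tested (SAP 4), so this estimate and its interval are the study's main result. An unstated choice that moved it materially would matter. Comparing arms would not cancel the error, because it acts on each arm's own late events.

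**Working it through.** The plan gives no event rate, arm size or precision figure, so there is nothing of its own to reproduce.

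**Inputs from the documents.** The 60-month window is 1825 ± 90 days, or day 1735 to day 1915. Of 505 subjects randomized, 75 were in an initial phase that closed in August 2010. The rest were randomized from July 2011 to March 2013, and extension enrolment began in April 2016 (Protocol 4.2).

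**Assumptions, since the documents give none.** 300 per arm; 1% a year, so the true 5-year risk is 1 − exp(−0.05) = 4.9%; visits spread evenly over the window; expanded-phase subjects only; no dropout; a quarter, half or all events found only at visits; missed earlier visits recovered from charts either fully or not at all.

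**1. The mechanism.** Suppose a share p of n completers has an event found at the 60-month visit, and m have been seen by the reading day. The expected sum of Kaplan-Meier jumps is p × (H(n) − H(n−m)), where H(n) = 1 + 1/2 + … + 1/n.

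- Half seen (day 1825): H(300) − H(150) = 0.69, so the contribution is 0.69p.
- All seen (day 1915): H(300) = 6.28, so it is 6.28p; for n = 120 it is 5.37p.

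The 0.69 is the curve's contribution relative to p. The share of events counted by then is one half.

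**2. Example at the window close.** Take 300 completers and 3 visit-detected events (1.0%). At the 75th, 150th and 225th visits the numbers at risk are 226, 151 and 76. The jumps are 0.44 + 0.66 + 1.32 = 2.4%. In random order the mean is 6.2% and the median 2.9%.

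**3. Simulated 5-year figure (truth 4.9%).**

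| Visit-detected share | Charts | Day 1825, mean | Day 1915, mean (median) |
|---|---|---|---|
| Half | none | 4.6% | 9.2% (6.8%) |
| Half | all | 4.7% | 7.4% (5.8%) |
| Quarter | none | 4.7% | 7.2% (5.8%) |
| Quarter | all | 4.8% | 6.4% (5.4%) |
| None | – | 4.9% | 5.1% (5.0%) |

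If every event is visit-detected and charts are recovered, day 1825 gives 4.5%. The sampling SD is √(0.049 × 0.951 / 300) = 1.25 points. If 60-month visits centre 30 days late, day 1825 gives 4.1% to 4.7%; 30 days early, 5.1% to 5.6%. The largest departure is 4.9 − 4.1 = 0.8 points, still under one SD.

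**4. Higher rates.** A separate simulation had 240 per arm, 3% a year dropout, follow-up from month 24 and every event visit-detected. Day 1825 gave 2.7%, 5.1% and 7.7% against true 3-year risks of 3.0%, 5.9% and 8.7%, at 1%, 2% and 3% a year. The shortfalls are 0.3, 0.8 and 1.0 points. The binomial standard errors √(q(1−q)/240) are 1.1, 1.5 and 1.8 points, so even this extreme stays near half a standard error.

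**5. Subjects followed longer.** From 31 August 2010 to 1 April 2016 is 2040 days, so any initial-phase subject who joined was already past day 1915. Protocol 8.2.3 provides for enrolment beyond 60 months. If the initial-phase share, 75/505 = 15%, held among 300, then 45 could remain at risk through the window. The multiplier at day 1915 then falls to H(300) − H(45) = 1.89, and the three-event example to 3/255 × 1.89 = 2.2%. How many joined, and how they would be censored, is not stated.

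**6. Would a written rule do better?** The obvious rule uses a recorded onset date where there is one and otherwise the nominal visit day, with onsets after day 1825 excluded. If sites record no onset for visit findings, it averages 4.8% to 4.9%. If sites enter the examination date as onset, findings after day 1825 drop out while completers stay at risk to day 1825. The contribution is then 0.5p, below 0.69p. With half the events visit-detected, the 5-year figure is 4.58%, against 4.69% with no rule.

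**The case for a change.** The best case for a change is that the omission is plain, the result affected is the primary one, and the remedy is a few sentences and one derived variable. Fixing conventions beforehand also prevents a choice made after seeing where late events fell. The window-close reading has some appeal because it keeps every valid 60-month examination. With half the events visit-detected and no charts, it exceeds 1.5 times the truth in 44% of simulated trials.

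The silence of the text stands, and so does the arithmetic for day 1915. What does not stand is that this is a likely reading. SAP 2, Protocol 8.2.3 and Protocol Appendix 1 all place month 60 at day 1825; the 90 days are attendance tolerance. The large day-1915 means are also driven by events among the last few at risk, which a printed number at risk would expose.

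Events dated after day 1825 are not lost from the report. SAP 5.2 has no day limit: "The number of subjects reporting at least one AE of a given type specified in the protocol will be summarized", and listings follow. Sight-threatening events are also serious events with expedited reporting (Protocol 10.5), which makes a documented date more likely, though not certain, for those that cause a complaint.

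Finally, moving visits to nominal days would have to be squared with SAP 6, which allows observed data only, and the rule would need extending to visits in the parent trial. It is a debatable convention, not a clear correction.

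**Conclusion.** No change follows. The three conventions are missing, but an analyst who takes 5 years as day 1825 and uses actual dates gets a sound estimate. Under the base assumptions it is about 0.1 to 0.4 points low on a true 4.9%, with an SD of 1.25. It stays within one SD if visits run 30 days early or late, and near half a standard error at 2% to 3% a year.

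The very different figures need four things together: a day-1915 reading, visit-dated events, completers censored at their own visit, and few subjects followed beyond it. The conclusion rests on assumed event rates, arm sizes, visit-detected shares and visit spread, none of which the documents give. It would weaken only if the curve were in fact read at the close of the window.
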